Individuals who are able/willing to participate

Individuals who are able and willing to participate will be asked to return their consent form and questionnaire to us. They will then be contacted within one month to schedule examination 1. If someone wishes to participate but is unable to complete examination 1, we will ask for their consent to use data from the questionnaire and link it to various registries.

Examinations

Questionnaire

Questionnaires will be labeled with barcodes to link them to individuals. The key that links barcode to personal identification number will only be stored in the database. The procedures for assigning project numbers, printing barcodes, and linking to personal identification number will be the same as previously used in HUNT3 (approved by REK and the Norwegian Data Inspectorate). In addition to being uploaded to the database by optical scanning, questionnaires will be stored at the research unit. Participants will receive a new questionnaire one year, three years, and five years after examination 1. The majority of questionnaire questions were used in HUNT3 (approved by HUNT Research Center).

Clinical examinations

Participants will be asked to attend medical examinations at baseline after one year, three years and five years. The following clinical tests will be performed:

- Medical screening with interview and checks of Consent signed
- Assessment of general health status

- Weight, height and waistline measurements
- Maximal oxygen uptake, maximal heart rate, heart rate 1 minute after testing

All data will be recorded both manually and electronically. A Case Report Form (CRF) will be completed for each participant, and forms will have a code linking the data to the participant. Forms will be entered into the project database by optical scanning. After scanning, forms will be locked and stored securely at the K.G. Jebsen Center for Exercise in Medicine, where only data supervisors will have access.

Links to registries

Participants consent to give the medical supervisor of Generation 100 access to medical records. In addition, we plan to connect our data to the Cause of Death Registry and Statistics Norway. Patient archive system of the community hospitals will be used to identify clinical outcomes (CVD and Cancer).

Follow-up

The participant may be contacted 10 years after inclusion of the study with a request to repeat basic examinations. Participation in follow-up examinations is voluntary.

Randomization

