The steering committee is the study's executive body. They have developed the study protocol and are responsible for data collection, management and publication. All major

scientific and ethical questions will be resolved by majority vote. The group is responsible for finding solutions to unforeseen questions/problems that arise in the course of the study. The steering committee consists of the following people: [name], PhD [name], MD [name], PhD [name], [name], [name], PhD and [name] [name], PhD.

Safety committee

All serious events that occur during the study should be reported to the research unit, which in return will report the event to a safety committee within one week. A research supervisor will fill out a safety report describing the event. Serious events are defined as: medical treatment resulting from the onset of new cardiovascular disease/events, or injuries/fractures. The committee will determine if the groups differ, and if it is ethically justifiable to let the study continue. Participants are encouraged to contact researchers if something unforeseen should occur; additionally, the safety committee will access the various registries once per year to obtain relevant data. The safety manager will be [name], Professor at the Department of Circulation and Medical (ISB), NTNU.

Funding

The project will primarily be funded by the K.G. Jebsen Center for Exercise in Medicine. Other major contributors include: Central Norway Regional Health Authority, the Norwegian Research Council, the Norwegian Association for Public Health, and NTNU.

Scientific significance and dissemination

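### The final protocol asks the safety committee to compare groups on injuries and fractures, but names no yearly source for non-fatal ones that is searched equally in all groups

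*Supplement*

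**What the plan says.** All references are to the final protocol.

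- **Safety committee, definition.** Serious events are "medical treatment resulting from the onset of new cardiovascular disease/events, or injuries/fractures". There are thus two classes: cardiovascular, and injuries or fractures.
- **Safety committee, task.** "The committee will determine if the groups differ, and if it is ethically justifiable to let the study continue".
- **Safety committee, inputs.** Serious events are to reach the research unit, which passes them on within a week with a written report. Participants are encouraged to make contact if something unexpected happens. In addition, "additionally, the safety committee will access the various registries once per year to obtain relevant data".
- **Links to registries.** The section opens with a general permission: "Participants consent to give the medical supervisor of Generation 100 access to medical records". It then says "we plan to connect our data to the Cause of Death Registry and Statistics Norway". On the hospital archive it says "Patient archive system of the community hospitals will be used to identify clinical outcomes (CVD and Cancer").
- **Examinations.** Questionnaires follow at years 1, 3 and 5. Examinations, with a medical interview and a general health assessment, take place at baseline and at years 1, 3 and 5. Neither is restricted by group.
- **Intervention.** The training groups return a log every month, may attend sessions with an exercise supervisor present, and have an obligatory supervised spinning session every sixth week. Controls are given the national recommendations and no further supervision.

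**The concern.** The yearly registry look is the only step in the safety text that does not depend on somebody choosing to report. It is what would make a comparison between groups fair. For injuries and fractures, the section that lists the data links offers nothing for it to draw on except deaths.

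Without a systematic source, what the committee sees depends on who is in contact with the study. Participants who meet staff regularly and post a log each month have more occasions to mention a fracture than controls do. An apparent excess in the training groups could then be a reporting artefact. A real benefit could also be hidden: the Physical activity section cites evidence that training reduces falls in older people at high risk, while noting that population-based studies are few. The direction of a true effect cannot be presumed, so the data should not lean either way. At stake is the committee's advice on whether the study may go on.

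**Working it through.** The plan gives no figure on this point, so there is none to reproduce. The check sets the event definition against every source of information in the final protocol.

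**Step 1. Sources for non-fatal injuries and fractures**

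| Source | Could show them? | Same in all groups? | Stated as a yearly input to the committee? |
|---|---|---|---|
| Cause of Death Registry | No, fatal injuries only | Yes | Not by name |
| Statistics Norway | No such use stated | Yes | Not by name |
| Hospital archive | Stated purpose is cardiovascular disease and cancer | Yes | No |
| Medical-record consent | Yes, not limited by diagnosis | Yes | No; no trigger, schedule or diagnosis list |
| Examinations and questionnaires | Possibly; injury items not shown | Yes | No; years 1, 3 and 5 only |
| Reports to the research unit | Yes | Open to all, but contact is unequal | Passed on within a week, not a systematic search |

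No row gives all three properties. The cardiovascular class is better placed, because the archive search names it, although the timing of that search for the committee is not stated either.

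**Step 2. Routine contact by group over five years**

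Inputs: monthly logs, spinning every sixth week, examinations at years 1, 3 and 5, and a five-year programme.

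- Logs, training groups: 12 × 5 = 60.
- Spinning sessions, training groups: (52 × 5) / 6 = 260 / 6 ≈ 43.
- Follow-up examinations, every group: 3.

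Scheduled contacts after baseline are therefore about 60 + 43 + 3 = 106 per training participant and 3 per control. This assumes full attendance and leaves out the voluntary group sessions and the information meeting. These are occasions on which an injury could come to light. The protocol does not say that the log asks about injuries.

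**Step 3. Consequence for the comparison**

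Let d_T and d_C be the probabilities that a treated injury becomes known to the committee in the training and control groups. Then

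observed rate ratio = true rate ratio × (d_T / d_C).

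A search run identically in all groups brings d_T / d_C towards 1. When detection depends on contact, Step 2 gives reason to expect d_T > d_C, which pushes the observed ratio upwards. The documents give neither probability, so the factor cannot be evaluated.

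**The case against.** The strongest reply is that the protocol has more routes than the registry list. Medical-record access is agreed by participants in every group and is not tied to a diagnosis. The examinations and questionnaires also apply to all. Serious events are meant to reach the research unit whatever their kind. All of this is correct. A reader might infer that the committee cannot see injuries at all, that no source is neutral between groups, or that only voluntary contact remains. The documents support none of these. Fatal injuries would also appear in the Cause of Death Registry.

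What the reply does not supply is a search. Consent to open records is a permission. The examinations leave years 2 and 4 uncovered, depend on attendance, and are not said to feed the committee.

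A second reply is that the short list may name only the sources for this study's own outcomes, with wider linkage continuing elsewhere. The Summary still speaks of linking to relevant registries for up to 20 years, and no listed amendment removes a registry. That reading is possible, so it would be wrong to conclude that patient or injury registry links were abandoned. The difference from the original protocol's longer list is not itself a fault. But the final protocol names no further registry, so its two sections still need to be reconciled.

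A third reply is that no primary or secondary outcome is touched. That stands, and it limits the weight of the point.

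**Conclusion.** The concern holds as a gap between two sections of the final protocol. Injuries and fractures are serious events on which the committee must compare groups, yet no named yearly source, searched alike in all groups, covers the non-fatal ones. This affects one of the two serious-event classes. With contact so uneven between groups, an injury comparison made as the protocol is written is open to ascertainment bias, more probably towards an apparent excess with training.

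The conclusion rests on two assumptions: that the Links to registries section is the operative list, and that record access, examinations and questionnaires are used only as stated. If wider linkage or a record review was in fact running, the remaining fault is that the protocol does not say so. The number of events that would be missed cannot be derived from the documents. The point is a worthwhile and inexpensive repair to safety monitoring. It does not threaten the mortality analysis.

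**What to change.** Reconcile the Safety committee and Links to registries sections:

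1. Add injury and fracture diagnoses to the hospital archive search already planned. Alternatively, schedule a medical-record review for them under the existing consent.
2. Run it once a year, with the same diagnosis list and the same look-back period in the high-intensity, moderate-intensity and control groups.
3. In the Safety committee section, replace the general reference to registries with the named source for each class of serious event.
4. Base the group comparison on events found by that search, and show spontaneously reported events separately.

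The cost is some extra data handling and possibly an approval amendment. No visit or assessor is added. One limit remains: an archive search would miss injuries treated only outside hospital. The same search rule would at least apply in every group.

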Participants are randomized (stratified by sex and cohabiting status) into one of two groups: an exercise training group or a control group. The exercise training group will again be randomized to either high-intensity training or moderate-intensity training. Spouses/partners will be randomized into the same group. The randomization will be performed after the completion of all basic examinations at examination 1. The Unit for Applied Clinical Research at NTNU is developing a web-based randomization procedure to ensure impartial assignments. After randomization, participants will receive verbal and written information about how to exercise and record their training.

Sample size and statistical power

The primary endpoint of the study is overall mortality. According to Statistics Norway, approx. 2% in this age group die every year. Currently, there is no data that indicates the magnitude of the effect of exercise on the reduction in mortality, but from observational studies a 50% reduction has been reported. With a 50% reduction in mortality rate, and a power of 90% (p<0.05), 1200 participants are needed (600 in each group). We will try to include 1500 participants to allow for drop-out (approximately 20%).

Intervention

Choice of intervention

Clinical studies have shown that high-intensity exercise training gives a greater increase in VO_{2max} and better cardiovascular adaptations than low- or moderate-intensity training (20, 22, 23). However, little research has been done on an elderly population, and it is unknown which intensity gives the greatest effect on morbidity, mortality and functional capacity in this group. Therefore, we believe that it is important to compare individuals who exercise at moderate and high intensities. Additionally, we think it is important to have a control group that receives current recommendations for physical activity.

High-intensity training group

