[name] were not able to be a part of the safety committee, thus [name] become the safety manager in the study. Changes made in June 2013.

Amendment No3.

By a mistake the outcome was change in July 2013. The reported outcome measures were related to the first PhD project, and instead of registering a new clinical trial, the candidate added the primary aims to the original trial. The mistake was noticed in May 2014, and the primary outcome was then changed back to what has always been the main outcome, mortality.

Amendment No4.

In August 2013 reasons for drop-out was changed to comprise; excluded, withdrew or died. Thus, participants who stops training for more than 6 months due to any reason, but still wanted to be in the study, were not excluded.

Amendment No5.

In October 2014, the principal investigators changed the primary aim to be more specific and clearer, and changed the secondary outcomes of the study to include changes in cardiovascular diseases, cancer, and peak oxygen uptake. Change in risk score, physical activity level, hospitalization, physical function capacity, medication, use of health care services, and development of dementia and depression will be presented in separate studies.

Original Statistical analysis plan

As specified in the protocol paper the primary combined endpoint of the study is overall mortality (24). Further, as described in the protocol paper (24); "All comparisons of change between the groups will be done by the intention-to-treat principle. Thus, data will be analyzed according to the group participants were assigned to, regardless of possible crossover and/or adherence to the intervention. Non-adherence will be defined as having performed less than 50% of the prescribed training sessions over the five years. Survival and morbidity analysis will be done by performing chi-square and log-rank tests. Cox regression analyses will be used to compute hazard ratios of all-cause mortality and onset of new diseases between the groups. The precision of the estimates will be assessed by 95% confidence intervals. All statistical tests will be two-sided."

Final Statistical analysis plan

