The original plan was not very specific on how the analysis would be performed; thus, a more detailed plan was formed before (13 February 2019) any analysis was conducted. For the VO_{2peak} and SF 8 we plan to use a linear mixed model with the clinical variables one at a time as dependent variable. Time point (0,1,3,5 years), intervention group, and their interaction as categorical covariates, and participant nested within cohabiting pair as random effects. Participants had been randomized such that a cohabiting pair was randomized to the same group. Hence, it is appropriate to use a three-level mixed model, with participant nested within cohabiting pair. In addition, we adjust for variables used as stratification variables in the randomization (sex, cohabitation status). We will adjust for age at inclusion, which is plausibly important prognostic factor, as recommended by (25) and (26). In the mixed model, we will adjust for baseline as recommended by (27). Normality of residuals will be checked by visual inspection of QQ plots. In these analyses, if a person is dead, we regard that as missing data after the person is dead. In a sensitivity analysis, we will exclude the persons who died during the study from the analysis. The main analysis for survival, will be a Cox proportional hazards regression, adjusting for the covariates listed above.

Summary of changes Statistical analysis plan

The following amendments to the original statistical analysis plan have been made.

• Amendment No1; Exclusion of VO_{2peak} data

Amendment No1:

Participants should have been tested on the same machine (treadmill or bike) at every examination. For those who had test both on treadmill and bike, we deleted the bike measurements. In total 41 persons had data both from treadmill and bike, bike measurements were deleted, and values given as missing.

References

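### The mixed model for VO2peak and SF-8 combines terms that do not fit together (year 0 as an outcome, a group main effect, baseline adjustment) and names no treatment contrast; on one natural reading its year-5 standard error is too small

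*Supplement*

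**What the plan says.** The model is described in the Final Statistical analysis plan, in one paragraph.

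- Outcomes: "For the VO_{2peak} and SF 8 we plan to use a linear mixed model with the clinical variables one at a time as dependent variable".
- Fixed and random terms: "Time point (0,1,3,5 years), intervention group, and their interaction as categorical covariates, and participant nested within cohabiting pair as random effects". Year 0 is thus an outcome visit, and group has both a main effect and an interaction with time.
- Levels: "Hence, it is appropriate to use a three-level mixed model, with participant nested within cohabiting pair".
- Other covariates: "In addition, we adjust for variables used as stratification variables in the randomization (sex, cohabitation status"), plus age at inclusion.
- Baseline: "In the mixed model, we will adjust for baseline as recommended by (27"). The form of adjustment is left to that cited paper.

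The paragraph does not say that the year-0 row or the group term is removed. It names no random slope and no residual covariance structure, and it does not say which coefficient or combination of coefficients is the treatment effect. Peak oxygen uptake is a secondary objective in Table 1 of the final protocol.

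**The concern.** A baseline value can be handled as an outcome or as a covariate. The SAP lists it as an outcome, with a group main effect that absorbs any baseline difference between groups, and then also promises to adjust for it.

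If the value is also entered as a covariate, each year-0 row has the same number on both sides of the equation. Those rows have almost no residual variance, yet they are pooled into the variance components that set the standard error at year 5. Confidence intervals for VO2peak and SF-8 would then be too narrow.

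The other ways of reading the text give different contrasts with different precision, so two analysts could follow the paragraph faithfully and report different results. Separately, random intercepts for pair and participant alone would force the year 0–5 correlation to equal the year 0–1 correlation, which is a strong assumption over five years.

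**Working it through.** **Inputs.** Visits, terms and random effects are from the Final Statistical analysis plan. The 5% level is stated only for the mortality sample size ("With a 50% reduction in mortality rate, and a power of 90% (p<0.05), 1200 participants are needed (600 in each group")), and two-sidedness only in the original SAP ("All statistical tests will be two-sided"); both are assumed here. The documents give no SD, correlation or standard error for VO2peak or SF-8, so there is no stated figure to reproduce and all correlations are assumptions.

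**Set-up for the algebra.** Complete data, unit variance at each visit, participant random intercept, no pair level, large sample, no true effect. Write r01, r03, r05 for the correlations of year 0 with years 1, 3 and 5. Sample size cancels from every ratio below. Type I error = 2Φ(−1.96 × SE ratio).

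**Reading A: baseline as covariate, adjusted year-5 difference (group + group × year 5).**

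1. Baseline does not vary within a participant, so its slope comes from participant means: b = (1 + r01 + r03 + r05)/4.
2. The model variance is the residual variance averaged over the four visits: 1 − b².
3. The true variance of the year-5 contrast is proportional to 1 + b² − 2b·r05.
4. With equal correlation r, b = (1+3r)/4 and the SE ratio is √[(15+9r)/(17+15r)].

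| Correlation | b | Model variance | True variance | SE ratio | Type I |
|---|---|---|---|---|---|
| equal, 0.5 | 0.625 | 0.609 | 0.766 | 0.892 | 8.0% |
| equal, 0.7 | 0.775 | 0.399 | 0.516 | 0.880 | 8.5% |
| equal, 0.8 | 0.850 | 0.278 | 0.363 | 0.875 | 8.6% |
| equal, 0.9 | 0.925 | 0.144 | 0.191 | 0.870 | 8.8% |
| falling 0.85, 0.825, 0.80 | 0.869 | 0.245 | 0.365 | 0.820 | 10.8% |
| falling 0.88, 0.80, 0.72 | 0.850 | 0.278 | 0.499 | 0.746 | 14.4% |

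A three-level REML simulation added the features left out above: 1,000 replicates; 1,560 participants, 520 of them in 260 pairs; 8%, 15% and 22% missing at years 1, 3 and 5. It was sized to the plan's target ("We will try to include 1500 participants to allow for drop-out (approximately 20"%)). SE ratios and type I errors were 0.891 and 7.6% (equal, 0.7), 0.881 and 7.7% (equal, 0.85), and 0.760 and 13.9% (falling to 0.7 at five years).

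**Reading B: only the group × year-5 interaction.** This compares year 5 minus year 0, so with complete data the baseline covariate cancels. What remains is a change-score comparison with variance proportional to 2(1−r), against 1−r² for baseline adjustment. The ratio is 2/(1+r): 1.25 at 0.6, 1.18 at 0.7, 1.05 at 0.9.

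The model variance is 2(1−m), where m is the mean of the six between-visit correlations. Under equal correlation m = r, so the ratio is 1.00 and type I error 5.0%. Under the two falling patterns, taken as linear in lag:

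- 0.85 to 0.80: m = 0.827; √(0.346/0.400) = 0.930; 6.8%.
- 0.88 to 0.72: m = 0.807; √(0.387/0.560) = 0.831; 10.3%.

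**Reading C: group main effect dropped (common baseline mean), no baseline covariate.** The estimate is the year-5 difference minus m times the baseline difference. Model variance is proportional to 1 − m², true variance to 1 + m² − 2m·r05. Under equal correlation the ratio is again 1.00 (5.0%). Under the falling patterns:

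- 0.85 to 0.80: √(0.316/0.361) = 0.936; 6.7%.
- 0.88 to 0.72: √(0.349/0.489) = 0.845; 9.8%.

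**Check of the remedy.** With years 1, 3 and 5 as outcomes and baseline as covariate, the closed-form SE ratio under equal correlation is 1.00 (5.0%), and the simulation gives 1.03 (4.5–4.6%). With random intercepts alone and falling correlation (0.6–0.8 at five years), the ratio is still 0.87–0.90 (7.6–8.8%). Removing the year-0 row is therefore not enough without a freer covariance.

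**The case against.** A reader might infer that the planned analysis will produce standard errors that are too small, full stop. The documents do not support that, for four reasons.

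- The form of baseline adjustment is delegated to a cited methods paper that is not part of the documents. Entering baseline as a covariate on the year-0 row is one reading; the SAP does not state it. Dropping the group main effect is also a form of baseline adjustment, and it is valid under equal correlation.
- The adjusted year-5 difference is not named as the contrast. The SAP names the interaction, and the original SAP speaks of comparing change between groups. The interaction keeps 5% under equal correlation, and its loss of precision is inefficiency, not invalidity.
- Random intercepts only is what the named terms plainly suggest, but the SAP does not use those words. Silence on the residual structure is not a commitment to equal correlation.
- The point estimate is hardly affected. In the scenarios tried, the true SE of the Reading A estimator is only 0.2–2.6% above that of a baseline-adjusted analysis of years 1, 3 and 5.

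All four stand, and they limit the claim. They do not remove it. The group main effect is listed, so Reading C contradicts the text; Reading B leaves the promised adjustment without effect; Reading A understates the SE. No reading delivers all that the paragraph states.

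**Conclusion.** The point holds as an incoherent model specification with an unnamed contrast; it should be fixed.

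The false precision is conditional. It is about 11–13% in the SE (type I error about 8–9%) if baseline is a covariate, year 0 stays in the outcome and the adjusted year-5 difference is reported, even when random intercepts are the true structure. It is about 18–25% (about 11–14%) if correlation also falls in the patterns assumed. The interaction and common-baseline readings are valid under equal correlation. They reach about 7–10% only if random intercepts are the whole covariance model and correlation falls with time.

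The direction for Reading A held in every scenario tried; the sizes depend on the assumed correlations. Only the mixed-model outcomes are affected: VO2peak, a listed secondary outcome, and SF-8. The Cox regression for all-cause mortality does not use this model.

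**What to change.** Replace the model sentences with one coherent specification, either:

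1. visits 0, 1, 3 and 5 as outcomes with a common baseline mean: no group main effect, group effects at years 1, 3 and 5 only, and no baseline covariate; or
2. visits 1, 3 and 5 as outcomes, with baseline and baseline-by-visit as covariates.

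In both, name the year-5 group difference as the treatment contrast, use an unstructured within-participant covariance over visits in place of the participant random intercept, and keep the random intercept for cohabiting pair. Sex, cohabitation status and age stay as planned.

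The cost is a short change to the SAP and a changed model call, with no new data. The unstructured matrix has 10 parameters for four visits or 6 for three, against 2 for a participant intercept plus residual. That is 8 or 4 more, which is trivial at the planned sample size.

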According to WHO, physical inactivity is the fourth major cause of premature death worldwide. Physical inactivity is an independent risk factor for death from cardiovascular disease, which is responsible for approx. 36% of all deaths in Norway. Physical activity is associated with a lower risk of developing diabetes (8), hypertension (9), depression (10), dementia (11), breast cancer (12) and colon cancer (13). There is also evidence that physical training lowers the incidence of falls in seniors with a high risk of falls (14). Nevertheless, there are few population-based studies on the effect of exercise training on risk of falling. Multiple epidemiological studies have shown that physical activity is associated with a reduced risk of premature death (15-17), and that individuals with high physical fitness live longer than individuals with low physical fitness (18, 19). Moreover, the data suggests that the greatest difference in risk of premature death is found in individuals who are inactive compared to those who report even a low level of physical activity (17). From a perspective of public health spending, it is important to note that individuals with a high fitness level experience more years of good health and self-reliance. Randomized, controlled studies have shown that regular exercise training increases fitness (20, 21), and improves several known risk factors for cardiovascular disease (22). Although we currently have evidence that physical activity improves cardiovascular risk profile and is important in maintaining physical capacity, the literature still lacks large randomized studies that document the effects of regular physical activity on morbidity and mortality.

Objectives

The main objective of this study was to, in a general population of older adults, test the primary hypothesis that 5-years of exercise training lowers all-cause mortality more than controls asked to follow physical activity guidelines given by national health authorities, and an exploratory hypothesis that high intensity training lower mortality more than moderate intensity training.

Additionally, we wish to see if there is a difference in change in development of cardiovascular disease and cancer between the groups. See Table 1 for primary and secondary objectives.

Primary objectives	Secondary objectives
Overall mortality	Death from cardiovascular disease
	Death from cancer
	Development of cardiovascular disease
	Development of cancer
	Peak oxygen uptake

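### The primary Cox model for mortality is valid but leaves baseline peak oxygen uptake unused; prespecifying it would bring a small gain in power and guard against a chance imbalance in fitness

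*Supplement*

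**What the plan says.** The Final Statistical analysis plan makes a Cox proportional hazards regression the main survival analysis and defines its covariates only by pointing back to those given earlier in the same paragraph. On the natural reading these are the two stratification variables (sex and cohabitation status) and age, of which the plan says "We will adjust for age at inclusion, which is plausibly important prognostic factor". Adjustment for a baseline value is mentioned only for the linear mixed models of VO2peak and SF 8. Baseline VO2peak is therefore outside the mortality model.

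Three places in the final protocol bear on this:

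- **Physical activity (background):** epidemiological studies are said to show that "individuals with high physical fitness live longer than individuals with low physical fitness".
- **Clinical examinations:** the tests at baseline and at one, three and five years include "Maximal oxygen uptake, maximal heart rate, heart rate 1 minute after testing".
- **Randomization:** "The randomization will be performed after the completion of all basic examinations at examination 1". Allocation is stratified by sex and cohabiting status, not by fitness.

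**The concern.** The plan accepts that an important prognostic factor belongs in the model and applies this to age, which by design spans only seven birth years (1936 to 1942). Fitness is the characteristic that the protocol's own background ties to survival. Its objective measure is recorded on the intended study population before allocation, so it is a legitimate baseline covariate. The plan gives no reason for taking one and leaving the other.

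Two things are at stake, both modest. Leaving a prognostic covariate out of a Cox model pulls the estimated hazard ratio slightly towards 1, which costs some power. And if the arms happen to differ in fitness, the part of that difference not explained by sex and age stays in the primary hazard ratio. Without a prespecified model, a visible fitness imbalance would invite a post hoc adjustment of the primary result.

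**Working it through.** **1. The plan's own sample size.** Inputs from the final protocol, Sample size and statistical power: "approx. 2% in this age group die every year", a 50% reduction, 90% power, p<0.05, 1200 participants, and 1500 to allow for about 20% drop-out. Follow-up for the primary hypothesis is 5 years. Sidedness comes from the original analysis plan ("All statistical tests will be two-sided"), which the final plan does not change.

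- Five-year risks: 5 × 2% = 10% against 5%. Two-sided comparison of proportions: 582 per arm, 1164 in total, within 3% of 1200.
- With 1 − 0.98^5 = 9.6% against half of that: 607 per arm, 1214 in total.
- Schoenfeld: 4 × (1.960 + 1.282)² / (ln 0.5)² = 87.5, so 88 deaths. At a mean risk of 7.5% this is 1174 participants.
- Drop-out: 1200 / 0.8 = 1500.

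The stated figure is reproduced. It assumes no covariates, so the point here does not alter it.

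**2. What adjustment gains.** The prognostic strength of VO2peak is not in the documents. I assume a mortality hazard ratio of 1.25 to 2.0 per SD lower VO2peak, meaning the part left after sex and age. Cox models were simulated with 1200 participants, a control 5-year risk of 10%, a true treatment hazard ratio of 0.5, a standard-normal covariate and 1500 runs per row.

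| HR per SD lower VO2peak | Estimated HR, without → with | SE of log HR, without → with | Power, without → with |
|---|---|---|---|
| 1.25 | 0.499 → 0.499 | 0.2234 → 0.2235 | 89.5% → 89.5% |
| 1.5 | 0.502 → 0.500 | 0.2238 → 0.2239 | 87.9% → 88.3% |
| 2.0 | 0.504 → 0.496 | 0.2233 → 0.2235 | 87.9% → 90.4% |

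The Monte Carlo error of each power is about 0.8 points. The standard error agrees with the expected deaths: 60 + 30 = 90, and √(1/60 + 1/30) = 0.2236.

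The gain in effective sample size is the ratio of squared z-values, less 1:

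- 1.25 per SD: (3.110 / 3.112)² = 1.00, no gain.
- 1.5 per SD: (3.096 / 3.079)² = 1.01.
- 2.0 per SD: (3.137 / 3.068)² = 1.045.

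Further simulation at 1200 to 1500 participants (about 87 to 123 deaths) gave about 0%, 1 to 2% and 4 to 5%. At a nominal 90% power, a 5% gain gives Φ(3.242 × √1.05 − 1.960) = 91.3%, or 1.3 points. The simulated differences above were 0 to 2.5 points with their Monte Carlo error, so roughly 0 to 2 points is a fair summary. At a true hazard ratio of 0.7 the changes were 40.6% → 40.7% (1.5 per SD) and 41.3% → 43.1% (2.0 per SD).

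**3. Chance imbalance at 750 per arm.** The SD of the between-arm difference is √(2/750) = 0.052 SD of VO2peak. Multiplying by the log hazard ratio per SD gives:

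- HR 0.6 per SD higher: 0.511 × 0.052 = 0.026. Two SDs move the treatment HR by exp(0.053) = 1.05.
- HR 0.5 per SD higher: 0.693 × 0.052 = 0.036. Two SDs give exp(0.072) = 1.07.
- HR 1.25 per SD lower: 0.223 × 0.052 = 0.012. Two SDs give exp(0.023) = 1.02.

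For comparison, 1500 participants give about 75 + 37.5 deaths, a standard error of √(1/75 + 1/37.5) = 0.20, and a 95% interval reaching a factor of exp(1.96 × 0.20) = 1.48 either way.

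**4. Missing baseline values.** If 5% lacked baseline VO2peak (assumed) and were dropped, power in the three rows of the table would be 87.9%, 86.4% and 88.3%. That is a net loss of about 1.5 points in the first two and a net gain of 0.4 in the third. With mean imputation plus a missing indicator and 8% missing (assumed), nearly all of the gain is kept.

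**The case against.** The case for leaving the plan alone is strong on validity. The covariates were fixed on 13 February 2019, before any analysis, and comprise both stratification variables plus age, with references. Randomisation protects the test and the interval. Calling one variable prognostic does not oblige the plan to include every prognostic variable measured. All of this stands.

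Three stronger readings are tempting and are not supported:

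- **That precision is lost.** In a Cox model the standard error stays the same (0.2233 → 0.2235 at 2.0 per SD). The gain comes from less attenuation of the hazard ratio. The width of the interval is set by the number of deaths.
- **That any fitness imbalance passes straight into the primary hazard ratio.** The part associated with sex and age is already absorbed. The interval also allows for chance imbalance: the share of sampling variance at stake is about 0.075 × (ln HR per SD)², or 0.4% to 3.6% over 1.25 to 2.0.
- **That the planned estimate is biased.** Nothing in the documents shows this.

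The assumed strength is also open to challenge. The background speaks of physical fitness, gives no effect size, and cites for this statement studies that, by their titles, concern men referred for cardiac rehabilitation and patients with heart failure. Heart failure is an exclusion criterion here. At 1.25 per SD the gain vanishes.

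Finally, VO2peak brings choices that sex, cohabitation and age do not: two test machines and missing values. The summary of changes to the analysis plan reports 41 persons with data from both machines whose bike values were set to missing, without saying at which visits. This is a real cost, but a rule can meet it.

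**Conclusion.** The point holds as a cheap efficiency improvement to a valid analysis. Baseline VO2peak is collected before allocation, fits the plan's own reason for adjusting for age, and is unused in the primary model. The benefit is about 0 to 5% in effective sample size (up to 0.05 × 1500 = 75 participants), or roughly 0 to 2 points of power, plus removal of the residual part of any chance fitness imbalance. An imbalance of 5 to 7% in the hazard ratio needs a 2-SD event and a strong association, and it is small beside an interval reaching about 48% either way.

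These sizes rest on an assumed prognostic strength. The simulations also ignore the clustering of cohabiting pairs and follow everyone for the full 5 years. The adjusted hazard ratio is conditional on fitness and so is a slightly different quantity (0.496 against 0.504 at 2.0 per SD); the difference is of no practical weight here.

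**What to change.** In the Final Statistical analysis plan, list the Cox covariates by name instead of by reference to the text above. Add baseline VO2peak as a continuous covariate with a treadmill/bike indicator. Use mean imputation plus a missing indicator, so that no randomised participant is dropped. Keep the model with sex, cohabitation status and age as a sensitivity analysis.

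One detail needs care. For this model, use the examination 1 value and machine as recorded, before the deletion of bike measurements. If a baseline bike value were removed because of a later treadmill test, the missing indicator would carry information from after randomisation, including survival to that test.

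The cost is a few sentences and two data rules; no new data are needed. If the primary model is to stay as it is, the VO2peak-adjusted model should at least be a prespecified sensitivity analysis.
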